Best Practice Alert (BPA) for Low Dose Aspirin Recommendation in High-Risk Pregnancies: a
Randomized Controlled Trial

Study Protocol with Statistical Analysis Plan

NCT05802940

06/05/2023

Study Protocol

Scientific Background

Preeclampsia is a significant cause of maternal morbidity and mortality, affecting up to 8% of pregnancies worldwide. Low dose aspirin (LDA) has been found to reduce the incidence of preeclampsia in high-risk pregnant patients.

Objectives

Upon internal review of electronic health record (EHR) data at our institution, we found that the recommendation for LDA use in high-risk pregnant patients was 60%. We hypothesize that the implementation of the EHR Best Practice Alert (BPA) will increase the healthcare provider's recommendation for LDA compared to the current standard care.

Design

We propose an RCT to assess the effect of an EHR clinical decision support (CDS) tool, specifically a BPA, on healthcare provider recommendations for low dose aspirin in high-risk pregnant patients.

Methods

Pregnant patients who receive and initiate prenatal care within Geisinger prior to 28 weeks gestation will be included if they are considered at high-risk of preeclampsia based on the modified United States Preventive Services Task Force (USPSTF) and American College of Obstetrics and Gynecology (ACOG) criteria listed above. Eligible patients will be randomized in a 1:1 fashion to a control or experimental group. In the control group, the women's health care provider will not receive a BPA; the pregnancy management will be based on the healthcare provider's current practice and knowledge. In the experimental group, the women's health care provider will receive a BPA in the EHR noting that the patient is at high-risk for preeclampsia and that the provider should recommend LDA. If LDA is not recommended, there will be a required acknowledgment reason from the provider noting a rationale for not initiating LDA. We defined women's health care provider as one of the following obstetric care providers who are able to prescribe medications: physicians (including resident physicians), physician assistants, certified registered nurse practitioners, and/or certified nurse midwives. Maternal-Fetal Medicine visits are excluded.

In the experimental group, when the BPA fires, the provider can either accept the BPA recommendations (to prescribe LDA and to add this medication to the medication list) OR the provider can reject the BPA. If the BPA is rejected, the provider must choose a reason for rejection, i.e., patient declined, patient allergic to aspirin, patient taking aspirin, patient does not meet ACOG criteria for LDA, and Other (with comment). These specific rejection reasons will be reviewed by study team members on an on-going basis, so that the algorithm can be updated if needed to ensure it is only applying to those patients for whom LDA should be recommended.

Power Analysis

A total of 640 patients will be required to yield an adequate power to show a statistically significant difference in LDA recommendation rate. However, we plan to enroll an additional 10% to account for possible early miscarriages and early terminations.

Project Status

Patients will be randomized to study arms as they showed up to their appointments with an anticipated start date of June 19, 2023. Data collection is ongoing until the primary outcome date of June 19, 2025 (after the conclusion of pregnancy for all enrolled patients).

Statistical Analysis Plan

Planned Analyses

Primary Outcome: *A sensitivity analysis of the healthcare provider recommendation for low dose aspirin use in patients, specifically those who deliver after 28 weeks*
[Time Frame: Assessed between initial prenatal visit and delivery after 28 weeks]

Outcome Description: Patient chart indicates that the provider recommended aspirin (yes/no) between the day of the initial prenatal visit and delivery (≥ 28 weeks). The outcome is captured either by aspirin being added to the patient's medication record or via a prespecified algorithm searching notes for text strings such as "LDA," "ASA," "baby aspirin," etc. As per ACOG, low dose aspirin therapy should be initiated between 12 and 28 weeks, therefore we limited this outcome to patients who deliver after 28 weeks to ensure the provider had the entire window that ACOG allows to make the recommendation for low dose aspirin initiation.

Question: Does a BPA, which identifies patients as HRPP and recommends and facilitates LDA prescribing, that fires during prenatal visits increase the likelihood of LDA recommendation/prescribing in comparison with no BPA firing?

Secondary Outcome: *The healthcare provider recommendation for low dose aspirin use in all randomized patients* [Time Frame: Assessed between initial prenatal visit and conclusion of pregnancy]

Outcome Description: Patient chart indicates that the provider recommended aspirin (yes/no) between the day of the initial prenatal visit and delivery (or conclusion of pregnancy). The outcome is captured either by aspirin being added to the patient's medication record or via a prespecified algorithm searching notes for text strings such as "LDA," "ASA," "baby aspirin," etc. This outcome will take into consideration all patients randomized, including those whose pregnancies resulted in termination, miscarriage or preterm delivery prior to 28 weeks. This intention-to-treat outcome will help assess the effect of the BPA in all patients.

Other pre-specified outcome measures

Outcome 1: *Patient taking low dose aspirin* [Time Frame: Assessed at time of delivery (≥ 28 weeks)]

Outcome Description: Patient chart indicates that the patient took aspirin (yes/no) during the pregnancy and up until delivery (≥ 28 weeks). The outcome is captured by aspirin being on the qualifying patient's medication record.

Outcome 2: *Rate of preeclampsia* [Time Frame: Assessed at time of delivery]

Outcome Description: Patient chart indicates that the patient experienced preeclampsia (yes/no) during the pregnancy, up until delivery. The outcome will be assessed at two time points, ≥ 28 weeks (so that patients were allowed the full window for low dose aspirin initiation) and ≥ 20 weeks (excluding miscarriages and earlier terminations of pregnancy). The outcome is captured by a diagnosis of preeclampsia on the qualifying patient's chart noted either by chart review or an algorithm that was created to capture this diagnosis.

Outcome 3: Timing of low dose aspirin recommendation [Assessed between initial prenatal visit to delivery (≥ 28 weeks)]

Outcome Description: Gestational age (in weeks) at the time that aspirin was first recommended (as indicated in the patient chart) between the day of the initial prenatal visit and delivery (≥ 28 weeks).

Outcome 4: Timing of low dose aspirin initiation [Assessed between initial prenatal visit to delivery (≥ 28 weeks)]

Outcome Description: Gestational age (in weeks) at the time that aspirin was initiated (as indicated in the patient chart) between the day of the initial prenatal visit and delivery (≥ 28 weeks)

Outcome 5: Preterm delivery [Time Frame: Assessed at delivery]

Outcome Description: Patient chart indicates that the patient experienced a preterm delivery (yes/no) during the pregnancy. The outcome will be assessed at two time points, ≥ 28 weeks (so that patients were allowed the full window for low dose aspirin initiation) and ≥ 20 weeks (excluding miscarriages and earlier terminations of pregnancy). The outcome is captured by a diagnosis of preterm delivery on the qualifying patient's chart noted either by chart review or an algorithm that was created to capture this diagnosis.

Outcome 6: Provider response to best practice alert [Time Frame: Assessed between initiation prenatal visit to delivery (≥ 28 weeks)]

Outcome Description: Data from the best practice alert will inform the study team of which responses are selected by the provider when responding to the best practice alert. Selection of prespecified responses by the provider will be reviewed on a weekly basis during the study period to assess whether the best practice alert triggering criteria needs to be adjusted.

Outcome 7: Number of times the best practice alert fired for a patient [Time Frame: Assessed between initial prenatal visit to delivery (≥ 28 weeks)]

Outcome Description: The BPA will stop firing once the BPA has been successfully addressed. Data from the BPA will inform the study team the number of times the BPA fired for a qualifying patient.

Analysis Notes

Recent work suggests that OLS regressions are appropriate in randomized experiments with binary outcome variables such as ours (Gomila, 2021).

Each analysis for the specified outcomes will be run using an OLS regression to examine whether the outcome differs as a function of experimental arm. For all analyses, if the distribution for a continuous outcome is positively skewed, a negative binomial or other appropriate model may be used instead.

As the treatment variation is at the individual level, we will report heteroskedasticity-robust standard errors. We will also explore the impact of clustering these standard errors at the clinic and clinic-date levels to allow for dependence across observations within these clusters. We will also investigate heterogeneity across clinics that vary along characteristics of interest, including prior-year recommendation rates.

References:

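### Eligibility caps gestational age when care begins, not at randomisation, so women already past 28 weeks can be randomised and kept in the primary analysis

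*Combined protocol and SAP*

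**What the plan says.** Four statements in the combined protocol and SAP bear on this.

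- **Entry** (Study Protocol, Methods): "Pregnant patients who receive and initiate prenatal care within Geisinger prior to 28 weeks gestation will be included". The 28-week limit attaches to receiving and starting care.
- **Randomisation** (Project Status): "Patients will be randomized to study arms as they showed up to their appointments with an anticipated start date of June 19, 2023". The sentence does not specify a first appointment, a new pregnancy or a gestational age.
- **Primary population** (SAP, Primary Outcome): "As per ACOG, low dose aspirin therapy should be initiated between 12 and 28 weeks". The outcome is then limited to women who deliver after 28 weeks, "to ensure the provider had the entire window that ACOG allows to make the recommendation for low dose aspirin initiation". The outcome itself is "Patient chart indicates that the provider recommended aspirin (yes/no) between the day of the initial prenatal visit and delivery (≥ 28 weeks"), so counting starts at the first visit, not at randomisation, and does not stop at 28 weeks.
- **Alert** (Outcome 7): "The BPA will stop firing once the BPA has been successfully addressed". No stop by gestational age is given.

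**The concern.** The restriction meant to secure the exposure works on gestational age at delivery. Whether the alert could act inside the window depends on gestational age at randomisation, which nothing in the text limits. At go-live, women already in care are at all stages of pregnancy, and those past 28 weeks satisfy the written rule if they booked before 28 weeks.

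Two things can happen in such a woman. Her aspirin decision may already be in the chart; it then counts in either arm and the alert cannot alter it, so the contrast between arms shrinks. Or the alert prompts a recommendation after 28 weeks; this counts as a success for the primary outcome but lies outside the window that the plan uses to justify that outcome. The first costs power. The second makes the result harder to interpret.

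**Working it through.** **1. The rules applied to one case.** Take a woman who booked at 9 weeks, first attends after go-live at 34 weeks and delivers at 39.

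| Rule | Her value | Met? |
|---|---|---|
| Care initiated before 28 weeks (Methods) | 9 weeks | yes |
| Attends an appointment from June 19, 2023 (Project Status) | 34 weeks | yes |
| Delivers after 28 weeks (Primary Outcome) | 39 weeks | yes |

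She is randomised and is in the primary population. Her provider spent 0 of the 16 weeks between 12 and 28 under a randomised allocation.

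**2. The plan's sample size.** Power Analysis gives 640. It cannot be reproduced, because the documents supply only the 60% current rate (Objectives) and 1:1 allocation (Methods); target rate, alpha, sidedness and power are not stated. Several assumed sets come close. For example, at two-sided 0.05, 60% against 70.5% with 80% power needs 644, and 60% against 72% with 90% power needs 652. I take 320 per arm, two-sided 0.05 and a treated rate of 70.55%, which gives about 80% power.

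**3. Dilution.** Let f be the share of analysed women past 28 weeks at randomisation. Assume the rate is 60% in both arms for them (no alert effect). The treated rate becomes

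p2(f) = 0.60 + 0.1055 × (1 − f)

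and, with n = 320 per arm and p̄ the mean of the two rates,

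power = Φ{ [ (p2 − p1)√n − 1.96 √(2p̄(1 − p̄)) ] / √( p1(1 − p1) + p2(1 − p2) ) }.

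At f = 0: (0.1055 × 17.889 − 1.96 × 0.6733) / 0.6692 = 0.848, so power is 80.2%.

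| f | Women of 640 | Treated rate | Power | Total N to restore 80.2% |
|---|---|---|---|---|
| 0 | 0 | 70.55% | 80.2% | 640 |
| 5% | 32 | 70.02% | 75.9% | 712 |
| 10% | 64 | 69.50% | 71.1% | 798 |

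If 640 was instead built for about 90% power (60% against 72.15%), the same shares give 90.3%, 87.0% and 83.0%.

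**4. If late alerts still work in part.** With a fraction r of the full effect in these women, f is replaced by f(1 − r). At f = 10% and r = 0.5 this is 5%, so power is 75.9% and not 71.1%. At r = 1 nothing is lost, but the extra recommendations fall after 28 weeks.

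The documents do not give f. The 10% enrolment allowance in Power Analysis is set aside for early pregnancy losses and was not sized for this.

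**The case against.** The best defence is that enrolment was meant to be early and the summary merely fails to say so. Much of this stands. The alert-response and alert-count outcomes are timed from the start of prenatal care, which fits randomisation at or near that point. The only enrolment allowance is for early losses. The high-risk criteria that Methods cites as listed above are not in the text supplied, and the alert algorithm is not described, so the EHR rule may hold a limit that this document omits. Rejection reasons are also reviewed weekly so that firing criteria can be adjusted, although that would not undo a randomisation. All this makes early enrolment plausible. None of it is an eligibility rule.

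It can also be said that an early booker's provider did have the whole window before go-live. That is true, but none of it was under allocation, so the window does not test alert against no alert.

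A reader might go further in three ways that the documents do not support.

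- **That the whole existing caseload enters in one block.** With booking at 9 weeks, delivery at 39 and steady intake, (39 − 28)/(39 − 9) = 37% of women in care at go-live would be past 28 weeks. Turning that into a share of the trial needs a weekly intake, which is not given, and the assumption that all of them attend and are randomised.
- **That the alert cannot affect these women's outcome.** It cannot act inside the 12 to 28 week window, but the outcome counts recommendations up to delivery. Zero effect is the worst case.
- **That the comparison is biased.** Allocation is randomised 1:1, so such women are expected equally in both arms. The effect is dilution.

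**Conclusion.** The point holds as a gap in the written eligibility rule. Read together, Methods and Project Status admit women first randomised after 28 weeks, and the primary restriction does not remove them, contrary to its stated purpose. The documents do not show that any were enrolled.

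This conclusion rests on the text alone. Its size is hypothetical: a loss of about 4 to 9 points of power for a 5% to 10% share, assuming 320 per arm, 60% against about 70.5%, two-sided 0.05 and no alert effect in these women. The loss is smaller if late alerts still produce recommendations, and nil if the EHR rule already excludes these women. The change is worth making because it is cheap and brings eligibility into line with the plan's own rationale.

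**What to change.** Add one condition to the inclusion rule and to the EHR randomisation logic: gestational age below 28 weeks at randomisation. State the visit at which randomisation may occur, and report gestational age at randomisation by arm. If enrolment has begun, use the same criterion to define the primary analysis population; it is fixed before allocation, so applying it to both arms keeps the comparison fair.

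**Cost.** Women past 28 weeks at go-live are not enrolled. With booking at 9 weeks, delivery at 39 and steady intake of L eligible women a week, that is (39 − 28) × L = 11L women, or about 11 more weeks of accrual if the whole caseload would otherwise have entered. Less is lost if it would not.

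The timetable can absorb this at a modestly higher intake. To have 704 women (640 × 1.10) delivered within the 104 weeks to June 19, 2025, enrolment of women at 9 weeks must end by week 104 − 30 = 74. The intake needed is:

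- whole caseload admitted: 704/(30 + 74) = 6.8 a week;
- below 28 weeks at randomisation: 704/(19 + 74) = 7.6 a week;
- first visit on or after go-live only: 704/74 = 9.5 a week.

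Do not adopt the last option. It discards about 30 weeks of intake and excludes women still inside the window, in whom the alert can act.

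The proposed condition does not guarantee the full window to a woman randomised at, say, 26 weeks, nor does it remove recommendations charted before randomisation in women already in care. The by-arm report will show how many women were randomised late in the window.

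### The randomisation visit is not defined and the outcome windows are not tied to it, so aspirin charted before assignment may count as a success in either arm (minor)

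*Combined protocol and SAP*

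**What the plan says.** **Randomisation.** Project Status gives the only timing: "Patients will be randomized to study arms as they showed up to their appointments", with an anticipated start of 19 June 2023. It does not say whether this is the first prenatal visit, the first visit at which the risk criteria are met, or the next visit of a patient already in care.

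**Eligibility.** Methods states "Pregnant patients who receive and initiate prenatal care within Geisinger prior to 28 weeks gestation will be included". This bounds when care began. It does not restrict entry to first visits or exclude patients already recommended or taking aspirin.

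**Outcome windows.** The primary outcome is a charted recommendation "between the day of the initial prenatal visit and delivery". The secondary outcome is "Assessed between initial prenatal visit and conclusion of pregnancy". Outcome 3 is "Gestational age (in weeks) at the time that aspirin was first recommended", again from the initial prenatal visit, and Outcome 4 (initiation) opens at the same point.

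**Capture and analysis.** A recommendation is detected from the medication record or a text search of notes, with no condition that the entry follow assignment. Analysis Notes specifies OLS of each outcome on arm and names no baseline covariate for earlier aspirin.

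**The concern.** The outcome clock and the randomisation clock are defined separately, and nothing makes them start together. Suppose a patient's first visit precedes her randomisation. A recommendation written at that first visit lies inside the outcome window but outside anything the alert could influence, and it scores as a success whichever arm she later joins.

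The text leaves room for two such patients: one already in care when the trial opens, and one who first meets the risk criteria at a later visit.

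At stake are the size of the estimated effect and the power to detect it. The primary question is whether a firing alert raises recommendation. Patients whose outcome was settled before assignment contribute a difference of zero and pull the estimate towards zero. For Outcomes 3 and 4, a gestational age fixed before assignment cannot respond to the alert.

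**Working it through.** **1. The plan's own figure.** Power Analysis gives 640 patients in total but no target rate, significance level, sidedness or numerical power, so 640 cannot be reproduced from stated inputs. With the 60% baseline from Objectives and a two-sided 0.05 test (assumed), 60% versus 70.5% at 80% power needs 644, and 60% versus 72% at 90% power needs 652. Either could lie behind the figure.

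**2. Inputs for the illustration.**
- From the documents: 640 patients allocated 1:1, so 320 per arm; baseline rate 60%.
- Assumed: two-sided 0.05; 60% versus 72% among patients not yet recommended at randomisation; a share *f* with an earlier charted recommendation, all scoring yes in both arms, with *f* at 0, 5%, 10% and 20%. The documents give no value for *f*.

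**3. Formulas.**
- Control rate = *f* + (1 − *f*) × 0.60
- Alert rate = *f* + (1 − *f*) × 0.72
- Difference = 0.12 × (1 − *f*)
- SE = √{[p₁(1 − p₁) + p₂(1 − p₂)] / 320}
- Power = Φ(difference / SE − 1.96)
- After exclusion: 60% versus 72% with 320 × (1 − *f*) per arm

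Example, *f* = 20%, all patients: rates 0.680 and 0.776; SE = √[(0.2176 + 0.1738)/320] = 0.0350; 0.096/0.0350 = 2.745; Φ(0.785) = 0.784.

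Same *f* after exclusion: n = 256; SE = √[(0.2400 + 0.2016)/256] = 0.0415; 0.12/0.0415 = 2.889; Φ(0.929) = 0.824.

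| *f* | Control | Alert | Difference | Power, all patients | n per arm after exclusion | Power after exclusion | Gain |
|---|---|---|---|---|---|---|---|
| 0 | 0.600 | 0.720 | 0.120 | 0.898 | 320 | 0.898 | – |
| 5% | 0.620 | 0.734 | 0.114 | 0.874 | 304 | 0.883 | 0.009 |
| 10% | 0.640 | 0.748 | 0.108 | 0.847 | 288 | 0.865 | 0.018 |
| 20% | 0.680 | 0.776 | 0.096 | 0.784 | 256 | 0.824 | 0.040 |

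Exclusion does not restore 0.90, because it also removes patients.

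**4. Adjusting instead of excluding.** Let V = 0.2400 + 0.2016 = 0.4416. If flagged patients all score yes, they add no variance once the flag is in the model. The adjusted difference is 0.12(1 − *f*), with variance about (1 − *f*)V/320. The ratio of estimate to SE is then 0.12√(1 − *f*)/√(V/320), the same as under exclusion. Adjustment therefore recovers about the same power while keeping everyone.

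**5. Sensitivity to the assumed rates.** The 60% in Objectives describes high-risk patients overall. Hold it as the overall control rate, and take a 10.56-point effect among the unflagged (about 80% power at 320 per arm when *f* = 0). At *f* = 20%, all patients: 0.600 versus 0.6845; SE = √[(0.2400 + 0.2160)/320] = 0.0377; power = Φ(2.238 − 1.96) = 0.61. After exclusion the control rate is (0.60 − 0.20)/0.80 = 0.50, against 0.6056, with n = 256; SE = √[(0.2500 + 0.2389)/256] = 0.0437; power = Φ(2.417 − 1.96) = 0.68. The loss and the gain are both larger here, but still rest on an *f* that nobody can read from the documents.

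**The case against.** The strongest reply is that the gap may be empty. The phrase in Project Status describes sequential enrolment and fits randomisation at the first prenatal visit, in which case both clocks start on the same day. Other text leans that way. Outcomes 6 and 7, which concern only the alert, are also assessed from the initial visit. The 10% extra enrolment is for early pregnancy losses, which suggests early entry. **This stands.** A reader might infer that randomisation occurs at whichever appointment a patient happens to attend, but the documents do not say so.

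A reader might also take the listed rejection reason that the patient is already on aspirin as proof of earlier recommendations. It is not. The alert fires until addressed, so she may have started between firings. She may also have been taking aspirin before her first visit for another reason.

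Finally, a reader might infer a bias in favour of the alert. With individual 1:1 randomisation, earlier recommendations are balanced in expectation, and the all-randomised contrast remains a valid, if diluted, intention-to-treat effect. Making exclusion the primary analysis would change the estimand to patients not yet recommended.

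What the reply does not remove is that no rule names the randomisation visit or ties the windows to it. Followed as written, the plan would count an earlier entry wherever one exists.

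**Conclusion.** The concern holds as a gap in definition, of minor severity. The randomisation visit is unstated, and the primary outcome, secondary outcome and Outcomes 3 and 4 are not anchored to it. The consequence is possible dilution and blurred timing outcomes, not bias towards the alert.

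The size cannot be determined from the documents. It is close to zero if randomisation is always at the first visit. Under the assumed 60% versus 72%, with 5% to 20% of patients affected, the recoverable power is about 1 to 4 points; under the less favourable rates in the sensitivity check it is about 7 points at 20%. All of these figures also assume a two-sided 0.05 test and no alert effect in patients already recommended.

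**What to change.** 1. State in Project Status and Methods at which visit randomisation occurs.
2. Start the windows for the primary outcome, the secondary outcome and Outcomes 3 and 4 at that visit.
3. Derive from EHR dates a flag for any aspirin recommendation or medication entry dated before randomisation.
4. Include the flag as a baseline covariate in the OLS models, keeping every patient the plan already analyses. The flag is fixed before assignment, so adjusting for it cannot bias the comparison.
5. Report the analysis restricted to unflagged patients as supplementary, including for Outcomes 3 and 4.
6. State one rule, applied identically in both arms, for scoring an earlier aspirin entry that is merely repeated or carried forward after randomisation. Moving the window does not settle this by itself, because the text search would pick up a repeated mention.

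The cost is SAP wording, one date comparison in data already held, and one extra covariate. If randomisation proves always to be at the first visit, few or no patients will be flagged and the results will barely change.

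### Restricting to deliveries after 28 weeks does not give every patient the whole 12–28 week window, and the timing models omit gestational age at entry

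*Combined protocol and SAP*

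**What the plan says.** - **Entry (Study Protocol, Methods).** "Pregnant patients who receive and initiate prenatal care within Geisinger prior to 28 weeks gestation will be included". No earlier limit on gestational age is given.
- **Randomisation (Project Status).** "Patients will be randomized to study arms as they showed up to their appointments".
- **The window (SAP, Primary Outcome).** "As per ACOG, low dose aspirin therapy should be initiated between 12 and 28 weeks".
- **The restriction and its reason (same section).** "therefore we limited this outcome to patients who deliver after 28 weeks", and this is done "to ensure the provider had the entire window that ACOG allows to make the recommendation for low dose aspirin initiation".
- **Repetition.** Outcome 2 (preeclampsia) and Outcome 5 (preterm delivery) justify their 28-week sets in the same way: "so that patients were allowed the full window for low dose aspirin initiation".
- **Timing outcomes.** Outcome 3 is "Gestational age (in weeks) at the time that aspirin was first recommended". Outcome 4 is the matching value for initiation. Both are assessed from the initial prenatal visit.
- **Models (Analysis Notes).** Each outcome is regressed on experimental arm by OLS with heteroskedasticity-robust standard errors. No baseline covariate is named. The only planned look at heterogeneity is across clinics.

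**The concern.** A window has two ends. Delivery after 28 weeks guarantees that the pregnancy lasted to the later end. Whether the provider also had the earlier part depends on when the patient entered care, and no restriction, stratum or covariate in the plan refers to that.

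Two things are at stake. The first is description. The restriction is the only reason given for making this set primary and placing the all-randomised comparison second, and a reader would take the primary estimate to describe patients who all had the full window. The second is precision. Outcomes 3 and 4 are measured on the gestational-age scale and counted from the first visit, so they contain entry age as a component that the alert cannot change. An arm-only model leaves that component in the residual.

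**Working it through.** **1. Share of the window left at entry.** The inputs are the window of 12 to 28 weeks (SAP, Primary Outcome), a length of 28 − 12 = 16 weeks, and entry at any time before 28 weeks (Methods).

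Weeks left = 28 − max(12, gestational age at entry). Share = weeks left / 16.

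| Entry (weeks) | Weeks left | Share |
|---|---|---|
| 12 or earlier | 16 | 100% |
| 16 | 12 | 75% |
| 20 | 8 | 50% |
| 24 | 4 | 25% |
| 26 | 2 | 12.5% |
| 27 | 1 | 6% |

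A patient who enters at 26 weeks and delivers at 39 belongs to the primary set. The stated property holds only for those who enter by 12 weeks.

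**2. Outcomes 3 and 4.** For a patient with a recommendation (or initiation) after entry:

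gestational age at event = gestational age at entry + delay from entry to event.

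Only the delay can respond to the alert. If delay is independent of entry age, then Var(outcome) = Var(entry) + Var(delay), and the share of variance due to entry is Var(entry) / [Var(entry) + Var(delay)]. The documents give no standard deviations, so the following are assumed:

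- Entry SD 4 weeks, delay SD 3 weeks: 16 / (16 + 9) = 64%. Full adjustment would multiply the standard error by √(1 − 0.64) = 0.60.
- Entry SD 3 weeks, delay SD 4 weeks: 9 / (9 + 16) = 36%. The multiplier is √(1 − 0.36) = 0.80.

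If patients who enter early also wait longer for a recommendation, delay and entry are negatively related and the gain is smaller.

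**3. Recommendation outcomes, illustration only.** The plan's total of 640 (Power Analysis) comes without a target rate, alpha or power, so it cannot be reproduced, and nothing here depends on it beyond n = 320 per arm. The control rate of 60% is from Objectives. Assumed values are a 10-point effect in early entrants, a 5-point effect in late entrants, and a late share L of 10%, 20% or 30%.

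Pooled effect = 0.10(1 − L) + 0.05L. Power is for the two-sided 5% two-proportion test with pooled variance under the null.

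| L | Pooled effect | Power |
|---|---|---|
| 0 | 10.0 points | 75.7% |
| 10% | 9.5 points | 71.2% |
| 20% | 9.0 points | 66.3% |
| 30% | 8.5 points | 61.2% |

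If late entrants respond as strongly as early ones, every row returns to 75.7%. The documents do not support choosing one case over the other.

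**The case against.** The strongest reply is that the sentence explains why pregnancies ending before 28 weeks are left out of the primary set, by contrast with the secondary outcome, which keeps them. On that reading only the word for completeness is loose, and removing it changes no analysis. This stands as far as the sentence goes, and rewording alone would be clerical.

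A reader might infer that late entrants bias the arm comparison. The documents do not support that. Entry age is fixed before 1:1 randomisation and is balanced in expectation, and chance imbalance is ordinary sampling error that the standard error already covers.

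A reader might also infer that the alert can hardly act in late entrants and that the trial therefore loses power. That does not follow either. At a single firing the provider must accept the alert or record a reason for rejecting it. The Outcome 7 description says that it stops firing once addressed, and no section says that it stops at 28 weeks. A recommendation at any time up to delivery counts. The effect in late entrants could even be larger, if unprompted providers miss more patients who have few visits. Weeks of window left therefore do not measure the alert's chance to work, and the average over all eligible patients is a legitimate target for a pragmatic trial of an alert.

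It is also fair to say that Outcomes 3 and 4 rank below the primary and secondary outcomes. That limits the weight of the point, but it is no reason to leave out a covariate that costs almost nothing.

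**Conclusion.** The mismatch is established from the documents alone: the 28-week delivery condition ensures that the window had closed before delivery, not that it was open throughout. Among eligible patients the share left at entry runs from 100% to nearly nothing. The number of patients affected is unknown, because the late-entry share is not given.

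The randomised comparison remains valid, and the power figures are illustrations resting on an effect size, a halved late-entrant effect and late shares that the plan does not state. The consequence that follows most directly is avoidable noise in Outcomes 3 and 4. Under the assumed standard deviations, entry age would account for 36% to 64% of the outcome variance. For the primary and secondary recommendation outcomes the gain from adjustment depends on how strongly entry age predicts a recommendation, which the documents do not show.

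**What to change.** 1. In Analysis Notes, pre-specify gestational age at randomisation (in weeks) as a baseline covariate in the OLS models for Outcomes 3 and 4, and in those for the primary and secondary recommendation outcomes. Keep the robust standard errors. If a negative binomial or other model replaces OLS for a skewed outcome, carry the covariate into it. Eligibility already requires gestational dating. Fix the choice before outcome data by arm are seen.
2. In the Primary Outcome, Outcome 2 and Outcome 5 descriptions, state that the restriction ensures only that the pregnancy was still ongoing when the window closed.
3. Optionally, add an exploratory analysis of the recommendation outcome by gestational age at entry, such as an arm-by-gestational-age interaction, with a note that it will be imprecise in a trial of this size.

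The cost is one covariate and a few sentences. Eligibility and sample size do not change. Adjustment does not cure a separate limit of Outcomes 3 and 4: a time exists only for patients who received a recommendation or started aspirin, a group formed after randomisation.
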